## LIST OF ABBREVIATIONS

AE	Adverse Event
CRF	Case Report Form
CRO	Clinical Research Organization
DCF	Data Clarification Form
DRM	Data Review Meeting
ESU	Electrosurgical Generator Unit
FAS	Full Analysis Set
FDA	Food and Drug Administration
GAIS	Global Aesthetic Improvement Scale
GCP	Good Clinical Practice
ICH	International Conference for Harmonization of Technical Requirements of Pharmaceuticals for Human Use
IFU	Instructions for Use
IPR	Independent Photographic Reviewer
IRB	Institutional Review Board
ITT	Intent-to-Treat
NRS	Numeric Rating Scale
NSAID	Non-steroidal Anti-Inflammatory Drug
PP	Per Protocol
PPS	Per Protocol Set
RF	Radiofrequency
SAE	Serious Adverse Event
SAL	Suction-Assisted Liposuction
UADE	Unanticipated Adverse Device Effect

## PROTOCOL SYNOPSIS

Protocol Title:	A Pilot Study of the Renuvion APR System when Used as an Adjunct Procedure in Gynecomastia Surgery
Investigational Device:	The Renuvion APR Handpiece (K191542) is a sterile, single use electrosurgical (monopolar) device intended to be used in conjunction with compatible generators for the percutaneous delivery of radiofrequency energy and/or helium plasma for cutting, coagulation and ablation of soft tissue. The Renuvion APR Handpiece is compatible with the Electrosurgical Generators BVX-200H/P (K170188), and APYX-JS3/RS3 (K192867) owned by Apyx Medical that are indicated for delivery of radiofrequency energy and/or helium gas plasma to cut, coagulate, and ablate soft tissue during open and laparoscopic surgical procedures.
Development Phase:	Pilot
Study Purpose:	To evaluate the use and safety of the Renuvion APR System as an adjunct procedure to bilateral gynecomastia surgery.
Brief Study Overview:	
This is a prospective, multi-center, single-blinded, randomized study of up to 10 study subjects undergoing bilateral gynecomastia surgery with Renuvion APR System used as an adjunct procedure on one side. The study will be conducted at up to 3 investigational centers in the United States.
 
At baseline, the grade of gynecomastia will be recorded by side, male chest measurements will be taken, and pre-surgery photographs taken in the frontal, lateral, and oblique views.
 
The gynecomastia surgery and Renuvion APR System use will be as per investigator's standard clinical practice. During the procedure, fat transfer and treatment of the lateral chest and/or axilla is not allowed. The Renuvion APR System will be used on one side only. The treated side will be randomized and the patient will be blinded as to which side of the chest received Renuvion. Procedure data and adverse events will be captured. Endermology is not allowed post-procedure. Post-procedure compression will be used for 2-3 weeks with a standard compression vest for all subjects.
 
Follow-up images, grade of gynecomastia, and male chest measurements will be taken at D30/D90/D180.
 
All images will be assessed for correct identification of Renuvion-treated side by blinded Independent Photographic Reviewers (IPR) following the D180 visit.
 
Following study participation, the subject will be offered an optional balancing treatment to the side not previously treated with Renuvion.

Number of Sites Enrolling Participants:	Subjects will be recruited from up to 3 study sites in the US.
Sample Size:	N = Up to 10 treated subjects; subjects enrolled may be greater than subjects treated.
Subject Population:	Healthy, male adult subjects, ages 18 – 75 years old who meet the inclusion/exclusion criteria.
Inclusion Criteria:	
 
1. Male subjects, ages 18 – 75 years old.
 
2. ASA Physical Status Classification System Class I and Class II subjects.
 
3. Clinical diagnosis of primary or secondary Gynecomastia.
 

	
 
4. Gynecomastia Rohrich Grade IIA or higher.
 
5. Symmetrical gynecomastia Rohrich grades.
 
6. Symmetrical chest measurements (no more than 3% variance between sides).
 
7. Scheduled for Gynecomastia surgery.
 
8. Willing to have Renuvion APR System as an adjunct procedure on one side understanding that an optional balancing procedure may be provided post-study exit.
 
9. Understands and accepts the obligation not to undergo any other procedures or treatments in the areas to be treated during study participation.
 
10. Absence of physical conditions unacceptable to the investigator.
 
11. Willing and able to comply with protocol requirements, including study-required images/photos, assessments/measurements, and returning for follow-up visits.
 
12. Willing to release rights for the use of study photos, including in publication.
 
13. Able to read, understand, sign, and date the informed consent.
 

Exclusion Criteria:	
 
1. Subjects without clinical diagnosis of primary Gynecomastia and/or a clinical diagnosis of gynecomastia with secondary causes such as medications, drugs, or testicular tumors.
 
2. Subjects presenting with ASA Physical Status Classification System Classes III or higher.
 
3. Gynecomastia Rohrich Grade I.
 
4. Non-symmetrical gynecomastia Rohrich grades.
 
5. Non-symmetrical chest measurements (more than 3% variance between sides).
 
6. Previous treatment or surgery in the breast area.
 
7. Active systemic or local skin disease that may alter wound healing.
 
8. Significant or uncontrolled medical condition that in the opinion of the investigator participation in the study may compromise the patient's health.
 
9. History of autoimmune disease (excluding Hashimoto's thyroiditis).
 
10. Known susceptibility to keloid formation or hypertrophic scarring.
 
11. Cancerous or pre-cancerous lesions in the area to be treated.
 
12. Possesses a surgically implanted electronic device (i.e. pacemaker).
 
13. Serious mental health illness such as dementia or schizophrenia; psychiatric hospitalization in the past two years.
 
14. Use of endermology post-procedure for the duration of the study.
 
15. Participation in any other investigational study within 30 days prior to consent and throughout study participation.
 
16. Subject who, in the opinion of the investigator, is not an appropriate candidate for the study.
 

Primary Safety Endpoint:	Analysis of bilateral occurrence of adverse events (both sides).
Outcome Measures:	
 
1. Bilateral analysis of change to STPTUP (Tebbetts & Adams High 5 Measurements) from baseline to day 30, 90, and 180.
 
2. Bilateral analysis of change to STPTIMF (Tebbetts & Adams High 5 Measurements) from baseline to day 30, 90, and 180.
 
3. Bilateral analysis of male chest measurements (Murphy) from baseline to day 30, 90, and 180.
 
4. Bilateral analysis of skin excised during the procedure by Gynecomastia Grade (Rohrich Classification).
 

	
 
5. Bilateral analysis of gland tissue removal methods (Longheu) during the procedure by Gynecomastia Grade.
 
6. The Principal Investigator, sub-investigator or qualified clinician delegated by the principal investigator, will complete a bilateral PGAIS assessing overall aesthetic improvement in the treatment area at day 30, 90, and 180 post-treatment.
 
7. The subject will complete a bilateral SGAIS assessing overall aesthetic improvement in the treatment area at day 30, 90, and 180 post-treatment.
 
8. The subject will complete a bilateral Patient Satisfaction Questionnaire (PSQ) at the 180-day follow-up visit.
 
9. Baseline images compared to Day 30, 90, and 180 images will be assessed for correct identification of Renuvion-treated side by blinded Independent Photographic Reviewers.
 

Safety Variables:	
 
1. Prior to treatment, the subject's medical history will be reviewed, and a physical examination will be conducted.
 
2. Following study treatment and at each subsequent visit, the subject will be queried about adverse events, expected treatment effects, and changes in concomitant medications, and the treatment area will be visually examined.
 

Study Duration:	The duration from when the study opens to enrollment until completion of data analyses is anticipated to be 12 months.

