#### **4.3 STUDY ENDPOINTS**

##### **4.3.1 PRIMARY SAFETY ENDPOINT**

The primary safety endpoint is the bilateral occurrence of adverse events.

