## 7.3 FOLLOW-UP PROCEDURES

### 7.3.1 IMMEDIATELY POST-PROCEDURE

All subjects will be required to wear a Sponsor-provided compression vest for 2-3 weeks.

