### 7.5.4 FOLLOW-UP

Subjects will be asked to return to the clinic for in-person follow-up visits at 30, 90, and 180 days post-treatment. At all visits, subjects will be assessed for safety and efficacy, images will be taken, adverse events and protocol deviations will be assessed, and study outcome measures (Gynecomastia Grade, STPTUP, STPTIMF, GAIS) will be completed. At the 180-day follow-up appointment in addition to the above referenced assessments, the subject will complete a Patient Satisfaction Questionnaire. Following study participation, the subject will be offered an optional balancing treatment to the side not previously treated with Renuvion. Virtual visits are not allowed for D30, D90, and D180 as images and measurements are required that are not able to be completed virtually.

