### 7.5.5 SAFETY ASSESSMENTS

Adverse events will be assessed immediately post-treatment and at all follow-up visits.

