## 8. ASSESSMENT OF SAFETY

### 8.1 SPECIFICATIONS OF SAFETY PARAMETERS

#### 8.1.1 DEFINITION OF AN EXPECTED TREATMENT EFFECT (ETE) AND AN ADVERSE EVENT (AE)

An expected treatment effect is defined as any typical treatment side-effect of Renuvion APR System of mild to moderate severity and lasting up to a typical maximum duration. An adverse event is defined as any new medical problem, or exacerbation of an existing problem, experienced by a subject while enrolled in the study, whether or not it is considered device-related by the investigator.

A preexisting condition (one that is present at the start of the study) will be recorded as an AE only if the frequency, intensity, or the character of the condition worsens during the study period. Neither the condition, hospitalization, prolonged hospitalization, nor surgery are reported as an AE in the following circumstances: hospitalization or prolonged hospitalization for diagnostic or elective surgical procedures for a preexisting condition. Surgery should not be reported as an outcome of an AE if the purpose of the surgery was elective or diagnostic and the outcome was uneventful.

All ETEs and AEs will be collected during the conduct of this trial.

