### 8.3 TIME PERIOD AND FREQUENCY FOR EVENT ASSESSMENT AND FOLLOW-UP

The occurrence of an AE or SAE may come to the attention of study personnel during a study visit or upon review by a study monitor. All ETEs and AEs will be captured on the appropriate CRF. Information to be collected includes event description, date of onset, clinician's assessment of seriousness and severity, relationship to study device/treatment (assessed only by those with the training and authority to make a determination), actions taken, and date of event resolution. All AEs occurring while on study must be documented appropriately regardless of relationship.

A pre-existing condition should not be reported as an adverse event unless there has been a substantial increase in severity or frequency of the problem that has not been attributed to natural history. Changes in the severity of an event will be documented to allow for a determination if the event should be re-categorized from an ETE to AE.

Safety evaluations for this study include an interview with the study subject at each follow-up visit by the Investigator or delegated study staff to elicit information about any medical occurrence that meets the definition of Adverse Event. This information will be documented in CRF without regard for cause or relation to device and/or procedure.

In addition, study subjects will be instructed in the Informed Consent Form, post-procedure take-home instructions, and verbally by study staff to report all complications experienced post study procedure to the site personnel as soon as they occur/are observed. Study staff will ensure that monitoring and management of all adverse events is prioritized.

Study investigators are provided liberty to mitigate adverse events as deemed necessary per IHC GCP Guidelines E6(R2)4.3.2 which states "During and following a subject's participation in a trial, the investigator/institution should ensure that adequate medical care is provided to a subject for any adverse events related to the trial".

Adverse event resolution dates will be determined by investigator using either in-person or remote (phone, video call, text, email, etc.) examinations or communication with the subject. To ensure the most accurate reporting of adverse event durations, investigators are instructed not to wait until scheduled office follow-up visits to assess resolution.

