It is the Investigator's responsibility to determine seriousness, severity, and relatedness of the Adverse Event to the device and procedure using the definitions in this protocol.

The PI will record all reportable events with start dates occurring any time after informed consent is obtained until 7 (for non-serious AEs) or 30 days (for SAEs) after the last day of study participation. At each study visit, the investigator will inquire about the occurrence of ETEs/AEs/SAEs since the last visit. Events will be followed for outcome information until resolution or stabilization.

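### No adverse event or expected-effect query is required between Day 0 and the Day 23-37 visit, so mild, short-lived events by side rest on volunteered reports or recall

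*Protocol*

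**What the plan says.** The primary endpoint in Protocol section 4.3.1 is a by-side safety comparison: "The primary safety endpoint is the bilateral occurrence of adverse events". Section 8.1.1 sets a broad collection aim: "All ETEs and AEs will be collected during the conduct of this trial".

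The timing of active questioning is consistent throughout the protocol:
- Synopsis, Safety Variables, item 2: "Following study treatment and at each subsequent visit, the subject will be queried about adverse events, expected treatment effects".
- Section 7.5.5: "Adverse events will be assessed immediately post-treatment and at all follow-up visits".
- Section 7.5.4: "Subjects will be asked to return to the clinic for in-person follow-up visits at 30, 90, and 180 days post-treatment".
- The schedule table in 7.3.2 marks adverse event assessment at the procedure and at the three follow-up visits, and gives the first visit a window of Day 23 to Day 37.
- Section 8.3 fixes the look-back at each visit: "the investigator will inquire about the occurrence of ETEs/AEs/SAEs since the last visit".

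For the time between visits, section 8.3 has subjects instructed "to report all complications experienced post study procedure to the site personnel as soon as they occur/are observed". Section 8.4.1 extends this to all AEs and says that AEs and ETEs observed by subjects or staff from first device exposure are recorded. Section 7.5.6 allows extra visits at the investigator's discretion, and section 14.1 has contacts that yield significant clinical information written into progress notes. On compression, section 7.3.1 states: "All subjects will be required to wear a Sponsor-provided compression vest for 2-3 weeks".

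**The concern.** Early local effects are the ones a side-by-side safety comparison of an energy device is most likely to show. Section 2.2.1 describes several ETEs, such as crepitus, migratory firmness and some sensory changes, as temporary or transient. An effect that starts after the subject leaves the procedure visit and settles before Day 23 is never the subject of a timely scheduled question. By the Day 30 visit the planned visual examination may find nothing.

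Timing also affects classification. Section 8.1.1 separates an ETE from an AE partly by how long the effect lasts, and section 8.3 wants changes in severity documented so that an ETE can be re-categorised as an AE. Both need onset, course and resolution. If these are reconstructed weeks later, an event near the boundary can be counted on the wrong side of it, which changes the count for the primary endpoint.

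Three errors are possible for mild, transient events: omission, poor dating and assignment to the wrong side of the chest. Omission understates incidence. Wrong-side assignment shrinks the difference between sides. A later analysis plan cannot recover data that were not collected.

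**Working it through.** **1. Reproduce the visit window.** Section 7.3.2 gives Day 30 ± 7, so the window runs from 30 − 7 = 23 to 30 + 7 = 37. This matches the schedule table. The other windows also agree: 90 ± 10 gives 80-100, and 180 ± 15 gives 165-195.

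**2. Length of the gap.** The last required query before the Day 30 visit is on Day 0. The interval without a required query is therefore 23 days at the shortest and 37 at the longest. Compression lasts 14 to 21 days and so falls wholly inside it.

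**3. Recall interval.** It depends on when the event starts. For onset on Day 1 it is 23 − 1 = 22 to 37 − 1 = 36 days. For onset on Day 14 it is 23 − 14 = 9 to 37 − 14 = 23 days.

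**4. What covers the gap.**

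| Provision | Section | Is it a solicited query? |
|---|---|---|
| Subjects report complications or AEs | 8.3, 8.4.1 | No, volunteered |
| Observed AEs and ETEs are recorded | 8.4.1 | No, applies once observed and made known |
| Unscheduled visits | 7.5.6 | No, discretionary |
| Significant contacts noted | 14.1 | No, documents a contact that happens |
| Resolution checked without waiting for a visit | 8.3 | No, for events already known |

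The title of section 7.3.2 refers to contact outside visits, but its text lists only the three visits.

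**5. Illustration of incomplete capture.** The documents give no event or capture rates, so both are assumed here. Let p be the true proportion of treated sides with an early event and c the share captured. With n = 10, the maximum in section 10.2, P(at least one recorded) = 1 − (1 − pc)^10.

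| p | c = 1 | c = 0.75 | c = 0.50 |
|---|---|---|---|
| 0.10 | 0.651 | 0.541 | 0.401 |
| 0.20 | 0.893 | 0.803 | 0.651 |
| 0.30 | 0.972 | 0.922 | 0.803 |

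For example, with p = 0.20 and c = 0.50: 1 − (1 − 0.10)^10 = 0.651.

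**6. Illustration of wrong-side assignment.** Let a and b be the true proportions on the treated and untreated sides, and let a share m of events on each side be assigned to the other. The observed proportions are a(1 − m) + bm and b(1 − m) + am. Their difference is (1 − 2m)(a − b). With m assumed at 10% the factor is 1 − 0.20 = 0.80, and at 25% it is 1 − 0.50 = 0.50.

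**The case against.** The strongest reply is that the schedule is coherent and the interval is not empty. Section 8.4.1 goes further than the instruction on complications in 8.3: subjects are told by several routes to report all AEs, and section 8.1.1 defines an AE widely. Unscheduled visits and significant contacts must be documented, and the synopsis wording about subsequent visits can be read to include unscheduled ones. Section 2.2.1 lists hematoma, seroma, burns and gas buildup separately from the ETEs, and subjects would be expected to report such complications promptly. The primary endpoint is adverse events, not ETEs. This is a descriptive pilot of up to 10 subjects with no hypothesis test.

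Most of that stands, and it limits the point to mild, transient events. It does not remove it, because none of these provisions requires anyone to ask the subject between Day 0 and Day 23.

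A reader might infer three stronger claims that the documents do not support:
- **That nothing is captured before Day 23.** Only required queries are absent; volunteered reports and noted contacts can supply events.
- **That the device would appear as safe as no device.** Under the formula in the working, 80% of the side difference survives at 10% wrong-side assignment, and it vanishes only at m = 50%. Nothing in the protocol suggests errors of that size.
- **That side is not asked for.** The data items in section 8.3 do not name it, but that list is not exhaustive, the CRFs are not shown, and the endpoint is itself defined on both sides.

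Nor does the protocol say that the vest hides events or hinders reporting. The vest period matters here only because it falls inside the gap.

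**Conclusion.** The point holds as a limited weakness in data collection. For 23 to 37 days after surgery, capture by side relies on volunteered reports, discretionary visits and noted contacts, followed by one look-back question. The events at risk are mild and short-lived, chiefly ETEs and events near the ETE/AE duration boundary. The likely directions are understated incidence and, where sides are confused, a smaller side difference.

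The gap length follows from the protocol's own figures. The size of any loss does not: the event, capture and wrong-side rates in the working are assumptions that show the range and estimate nothing for this trial. The expectation that serious or marked events would be reported promptly is a judgement, though one the reporting instructions support. The protocol does not contradict itself here, and the change is a cheap improvement rather than a condition for running the study.

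**What to change.** In section 7.5.5 and the schedule table, add one structured remote AE/ETE query during the vest period. Phone, video, text and email are already accepted in section 8.3 for establishing resolution dates. Ask about each effect for right, left or no side, and record onset and resolution dates. Word the questions as right and left, never as device and comparison side, so that the subject stays blinded. The query collects data only and changes no care.

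The cost is about ten short contacts in total (one for each of up to 10 treated subjects), one CRF page and a protocol wording change. Recorded event counts will probably rise. The query shortens the recall interval without removing it.

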## 1. KEY ROLES

Persons, companies, and/or groups serving in key roles in the conduct or oversight of this clinical trial are listed in **Table 1** below, including sponsor, clinical project manager for the trial, investigator responsible for conducting the trial.

## 2. INTRODUCTION: BACKGROUND INFORMATION AND SCIENTIFIC RATIONALE

### 2.1 BACKGROUND INFORMATION & RATIONALE

Energy has been applied in some form to tissue since the beginning of recorded history. The practice of applying heat to tissue through the use of cauteries was used for thousands of years as an invaluable method of controlling hemorrhage. Continuous improvement of methods for utilizing the beneficial effects of heat on tissue eventually led to the development of the basic concepts of electrosurgery we know today. In October of 1926, [name] used an electrosurgical unit developed by [name] to successfully remove a highly vascularized brain tumor from a patient after previous failed attempts. Today, electrosurgical instruments are used in almost every surgical procedure performed worldwide.

Through this long history, the heat effects of the radiofrequency (RF) alternating current used in electrosurgery on cells and tissue have been well established. Normal body temperature is 37°C and, with normal illness, can increase to 40°C without permanent impact or damage to the cells of our body. However, when the temperature of cells in tissue reaches 50°C, cell death occurs in approximately 6 minutes. When the temperature of cells in tissue reaches 60°C, cell death occurs instantaneously. Between the temperatures of 60°C and just below 100°C, two simultaneous processes occur. The first is protein denaturation leading to coagulation which will be discussed in more detail below. The second is desiccation or dehydration as the cells lose water through the thermally damaged cellular wall. As temperatures rise above 100°C, intracellular water turns to steam and tissue cells begin to vaporize as a result of the massive intracellular expansion that occurs. Finally, at temperatures of 200°C or more, organic molecules are broken down into a process called carbonization. This leaves behind carbon molecules that give a black and/or brown appearance to the tissue.

Understanding these heat effects of RF energy on cells and tissue can allow the predictable changes to be used to accomplish beneficial therapeutic results. Protein denaturation leading to soft tissue coagulation is one of the most versatile and widely utilized tissue effects. Protein denaturation is the process in which hydrothermal bonds (crosslinks) between protein molecules, such as collagen, are instantaneously broken and then quickly reformed as tissue cools. This process leads to the formation of uniform clumps of protein typically called coagulum through a subsequent process known as coagulation. In the process of coagulation, cellular proteins are altered but not destroyed and form protein bonds that create homogenous, gelatinous structures. The resulting tissue effect of coagulation is extremely useful and most commonly used for occluding blood vessels and causing hemostasis.

In addition to causing hemostasis, coagulation results in predictable contraction of soft tissue. Collagen is one of the main proteins found in human skin and connective tissue. The coagulation/denaturation temperature of collagen is conventionally stated to be 66.8°C, although this can vary for different tissue types. Once denatured, collagen rapidly contracts as fibers shrink to one-third of their overall length. This principal of thermally-induced contraction of collagen through denaturation and coagulation of soft tissue is well known in medicine and is used to achieve beneficial results in ophthalmology, orthopedic applications, and the treatment of varicose veins. Once tissue is heated to the appropriate temperature, protein denaturation and collagen contraction occur resulting in a reduction of volume and surface area of the heated tissue. Noninvasive use of RF devices, lasers, and plasma devices have been used for the reduction of facial wrinkles and rhytides caused by thermal-induced collagen/tissue contraction since the mid-1990s.

Recently, the use of thermal-induced collagen/tissue contraction has been expanded to minimally invasive procedures. Laser-assisted lipolysis (LAL) and radiofrequency-assisted lipolysis (RFAL) devices have combined the removal of subcutaneous fat with soft tissue heating to address the skin laxity that often results from fat volume

removal. These devices are placed in the same subcutaneous tissue plane as a standard suction-assisted lipolysis (SAL) cannula and are used to deliver thermal energy to coagulate the subcutaneous tissue including the underside of the dermis, the fascia, and the septal connective tissue. The coagulation of the subcutaneous tissue results in collagen/tissue contraction.

Apyx Medical Corporation's product family of helium-based plasma technology (Renuvion/J-Plasma family of devices) has FDA clearance for the cutting, coagulation, and ablation of soft tissue. The Renuvion APR Handpiece is a new device designed to be a part of this helium-based plasma technology family. All devices in the product family are part of a system that consists of an electrosurgical generator unit, a handpiece, and a supply of helium gas. RF energy is delivered to the handpiece by the generator and used to energize an electrode. When helium gas is passed over the energized electrode, a helium plasma is generated which allows heat to be applied to tissue in two different and distinct ways. First, heat is generated by the actual production of the plasma beam itself through the ionization and rapid neutralization of the helium atoms. Second, since plasmas are very good electrical conductors, a portion of the RF energy used to energize the electrode and generate the plasma passes from the electrode to the patient and heats tissue by passing current through the resistance of the tissue, a process known as Joule heating. These two sources of tissue heating give the Renuvion APR device some advantages during use as a surgical tool for the coagulation and contraction of subcutaneous soft tissue.

These advantages are as follows:

1. The Renuvion APR Handpiece device achieves soft tissue coagulation and contraction by rapidly heating the treatment site to temperatures greater than 85°C for between 0.040 and 0.080 seconds.
2. The tissue surrounding the treatment site remains at much cooler temperatures resulting in rapid cooling after the application of the energy through conductive heat transfer.
3. Focused delivery of energy on immediate heating of the fibroseptal network resulting in immediate soft tissue coagulation and contraction without unnecessarily heating the full thickness of the dermis.
4. 360° tissue treatment without the need for the user to redirect the flow of energy due to electrical energy taking the path of least resistance.
5. Unencumbered delivery of power regardless of the tissue impedance due to the unique power output from the electrosurgical generator.
6. Low current RF energy resulting in minimal depth of thermal effect and prevention of over-treating tissue when performing multiple passes.

Gynecomastia is a benign enlargement of the male breast due to proliferation of the glandular tissue. It affects up to 65% of males at all stages of life, however, not all require surgical intervention. Typically, gynecomastia presents as asymmetric and mostly bilateral. Treatment options are varied, but liposuction, either alone or in conjunction with removal of the glandular tissue, is most commonly utilized. This study aims to evaluate the use and safety of the Renuvion APR System as an adjunct procedure to bilateral gynecomastia surgery.

